## LIST OF ABBREVIATIONS AND RELEVANT DEFINITIONS

AE	Adverse Event	
AR	Adverse Reaction	
ССМО	Central Committee on Research Involving Human Subjects; in Dutch:	
	Centrale Commissie Mensgebonden Onderzoek	
CAD	Computer Aided Detection	
CRF	Case Report Form	
CXR	Chest X-ray	
EDC	Electronic Data Capture	
EU	European Union	
тв	Tuberculosis	
GCP	Good Clinical Practice	
GDPR	General Data Protection Regulation; in Dutch: Algemene Verordening	
	Gegevensbescherming (AVG)	
IC	Informed Consent	
MGIT	Mycobacteria Growth Indicator Tube (BD Products)	
MREC	Medical research ethics committee (MREC)	
NAAT	Nucleic Acid Amplification Test, for example GeneXpert ®	
PIF	Participant Information Form	
PNCT	Programa Nacional de Control de la Tuberculosis (National TB	
	Program)	
PPL	Personas Privadas de Libertad / people deprived of liberty, prisoners	
POC	Point-of-care	
PRONASIDA	Programa Nacional de Control de VIH-sida (National HIV Program)	
Sponsor	The sponsor is the party that commissions the organisation or	
	performance of the research, for example a pharmaceutical	
	company, academic hospital, scientific organisation or investigator. A	
	party that provides funding for a study but does not commission it is	
	not regarded as the sponsor, but referred to as a subsidising party.	
WMO	Medical Research Involving Human Subjects Act; in Dutch: Wet	
	Medisch-wetenschappelijk Onderzoek met Mensen	
WHO	World Health Organization	

#### SUMMARY

Rationale: Despite being a curable disease, each day thousands of people die of tuberculosis (TB) worldwide. TB diagnosis is often delayed, increasing the likelihood of transmission. The aim of the World Health Organization (WHO) "End TB Strategy" is to end the global pandemic by 2035. To be able to succeed, better point-of-care (POC) tests are urgently needed to improve screening of high-risk populations. Prisons are recognized worldwide as high risk environments for the concentration, amplification and transmission of TB among prisoners and their communities outside. Paraguayan penal institutions are known to have very high incidence rates of active TB (3000-5000/100.000, according to Paraguayan Ministry of Justice). Two diagnostic tools for TB screening in high risk groups need additional validation: the AeoNose™, an 'electronic nose device' for breath sampling, and digital chest X-ray (CXR) with computer aided detection with CAD4TB® software. This study will systematically screen prisoners and its' employees for TB, test the diagnostic performance of AeoNose™ and CAD4TB® and assess prison *Mycobacterium tuberculosis* epidemiology through several objectives: **Objective**: 1. Assessment of the sensitivity and specificity of the AeoNose™ and its utility for mass TB screening in high incidence settings. 2. Evaluation of the feasibility and utility of CAD4TB® digital CXR as a mass screening tool for TB. 3. Identification of factors that affect diagnostic accuracy of AeoNose™ and CAD4TB®. 4. Assessment of TB epidemiology in Paraguayan prisons and identification of mycobacterial strains. 5. Assessment of cost effectiveness of different screening algorithms. 6. Characterization of transmission dynamics and potential measures for transmission reduction. Study design: Diagnostic cohort study. Study population: Detainees (PPL) of Paraguayan penal institutions as well as their employees. Main study parameters/endpoints: 1. Number of TB cases diagnosed with GeneXpert® and/ or culture of Mycobacterium tuberculosis complex. 2. Number of TB cases correctly identified by AeoNose™. 3. Number of TB cases correctly identified by CAD4TB®. 4. Costs and effectiveness of different screening algorithms. 5. Mycobacterium tuberculosis complex

strains identified with Whole Genome Sequencing. Nature and extent of the burden and risks associated with participation, benefit and group relatedness:

Individual burden: all participants will perform one visit with a medical doctor for medical history, physical exam, digital X-ray (with CAD4TB®) and AeoNose sampling. Participants will be offered voluntary HIV testing and counseling. In case of presumptive TB (estimated 20-30% of participants) two sputum samples will be taken, either spontaneous or saline-induced. One sample is tested with GeneXpert and the other with liquid mycobacterial culture. Cases of presumptive TB with both negative GeneXpert® and culture results will be followed-up after three and six months for repeat testing.

Individual and group health benefit: all participants will have a medical consultation and CXR. In case of an alternative diagnosis, the prison health service will be notified. People diagnosed in the study with active TB will be notified and referred to receive treatment through the PNCT according to national guidelines. All participants will eventually benefit from less exposure to infectious TB cases through optimized infection control measures and treatment of infected individuals. The study will provide the PNCT with epidemiological data of this vulnerable group to optimize future TB control strategies.

#### Long-Term Benefit:

After the study, the Ministry of Health will have an accurate update on the incidence of TB in the three involved prisons. Based on this information, more effective strategies can be designed for TB elimination in Paraguayan prisons.

The Ministry of Health (department of telemedicine - PNCT) will receive the mobile digital Xray machine and CAD4TB software that can be used throughout the country, especially in vulnerable groups and people living in remote areas.

#### 1. INTRODUCTION AND RATIONALE

Every day, over 4700 people die of tuberculosis (TB). The aim of the World Health Organization (WHO) "End TB Strategy" is to stop the global TB pandemic by 2035. (WHO, Geneva 2010) TB is a curable disease, but frequently remains undiagnosed, leading to ongoing transmission, infection and suffering. More accurate and affordable point-of-care (POC) tests are urgently needed that are suitable for the low resource settings in which TB is most prevalent. The pandemic is driven by transmission, which occurs not only from known TB patients but also from persons with unsuspected TB or ineffective TB treatment. The former WHO strategy of screening only symptomatic persons with (low-sensitive) sputum smear microscopy needs to be changed drastically as many TB cases remain undiagnosed.

Target product profiles for new TB screening tools and diagnostics were devised stressing the high priority of a systematic screening test for active case finding. (WHO Consensus meeting report, Geneva 2014). New POC screening tests should rapidly identify high likelihood individuals to select them for subsequent laboratory tests that can confirm active disease. A cheap and rapid POC test can improve the efficacy and efficiency of screening algorithms by optimizing the use of expensive and time-consuming tests such as nuclear acid amplification tests (NAAT) or sputum mycobacterial culture.

A promising POC diagnostic tool is the AeoNose™; an electronic nose device. (The eNose Company, Zutphen, the Netherlands). The AeoNose™ works with three metal oxide sensors which gather 'smell prints' of volatile organic compounds in the subject's breath. The collected vectors are sent via internet to a central computer and then compared to a neural network of TB breath profiles. After establishing a validated neural network, new breath profiles can be analyzed within minutes. The device is battery-powered, handheld and lightweight, making it very suitable for POC use.

The AeoNose™ showed promising results as a TB diagnostic tool in previous studies in Bangladesh and Paraguay. (Bruins, Tuberculosis 2013; Coronel Teixeira, J Infect 2017) Like digital CXR and CAD, an electronic nose device could be implemented in a screening algorithm to "rule in" subjects for further testing. This could bring improvements of case finding and infection control, efficiency and reduced costs. Before the AeoNose™ can be brought to the market the technology needs to be further tested and the neural network needs to be validated in a large high-incidence population.

Abnormalities corresponding with TB can be detected early on CXR, even in asymptomatic participants. The WHO now recommends to add CXR to screening algorithms (WHO,

Geneva 2013). Conventional X-ray technology is available even in many low-income countries, although imaging quality is often poor and systems need expensive X-ray films and skilled personnel to interpret results. Digital X-ray with computer-aided detection (CAD) has many advantages over conventional X-ray and is considered very promising for TB mass screening programs. A mobile digital X-ray laboratory with CAD has been developed and has already been used in several screening programs in high-incidence settings. (E.g. Philipsen, Sci Rep 2015) CXR is used to identify participants with presumptive TB and subsequently sputum is obtained for culture or a rapid molecular test (NAAT/GeneXpert®). Figure 1, adapted from Khan et al. (Eur Resp J 2017), illustrates the logistics of screening with CXR in either symptomatic participants (a) or mass screening in a vulnerable group or community (b).

Figure 1. Screening in (a) symptomatic subjects or (b) a vulnerable group or community. Source: Khan et al. Eur Resp J 2017.

Currently, there are three commercially available CAD systems to detect TB on CXR that show no significant differences in performances. (Qin et al., NatureResearch-scientific reports 2019) CAD4TB® by Delft Imaging Systems (Veenendaal, the Netherlands) was

developed in collaboration with the Diagnostic Image Analysis Group from Radboud University Medical Centre (Prof. dr. [name]). The CAD4TB® software has already been adopted for screening purposes, including studies in prisons. The newest software version (version 6) performs as good as skilled human readers, with a high sensitivity of 95% and excellent negative predictive values (NPV) as well as specificity of 70%, depending on the selected threshold value of the output score. (Melendez, Int J TB Lung Dis 2018) Still, there is evidence lacking for WHO-endorsement for CAD as part of large screening programs. (Khan, Eur Resp J 2017) Most importantly, an optimal threshold value of the output score must be identified for different population and patient characteristics. Additionally, CAD needs to be compared against skilled human readers, and safety and ethical issues need to be addressed concerning the incidental detection of lung malignancies and other non-TB pathology. Finally, the large-scale implementation of such technology needs to be evaluated from a health-economic viewpoint.

Setting: Prisons worldwide are high-risk environments for the concentration, amplification and further transmission of TB among prisoners, employees and the communities outside the prison. Sanitary conditions and healthcare services in prisons are often poor. Addressing the unmet healthcare needs of prisoners is crucial to achieve the goal of global tuberculosis control. (Kamarulzaman, Lancet 2016; Dara, Int J ID 2015) Paraguayan penal institutions also count with very high estimated incidence rates of active TB (3000-5000/100.000). Currently, since the assembly meeting in New York in 2018, reduction of TB incidence and transmission is a top priority for the Paraguayan Ministry of Health and the PNCT. In this study proposal, we aim to perform a mass TB screening in Paraguayan prisons using AeoNose™ and CAD4TB® and assess their utility for future screening algorithms.

#### 2. OBJECTIVES

Primary Objective:

- Assessment of the sensitivity and specificity of the AeoNose™ and its utility for mass TB screening.
- 2. Evaluation of the feasibility and utility of CAD4TB® digital CXR as mass screening tool for TB in high incidence settings.
- 3. Identification of factors that affect diagnostic accuracy of AeoNose™ and CAD4TB®.

Secondary Objective(s):

- 1. Assessment of TB epidemiology in Paraguayan prisons and identification of mycobacterial strains.
- 2. Assessment of cost-effectiveness and cost-efficiency of mass screening programs integrating digital CXR with CAD4TB®, AeoNose™ or both techniques in conjunction.
- 3. Characterization of transmission dynamics and potential measures for transmission reduction.

## 3. STUDY DESIGN

Diagnostic prospective cohort study: mass screening through conventional symptoms screening by a doctor, a physical exam and with testing of CAD4TB® and AeoNose™ as well as bacteriological testing of presumptive cases.

An estimated 5000 individuals will be invited to participate. All prisoners and employees will be eligible for inclusion. The sample size is based on an estimated incidence of 3000-5000/100.000 and a presumptive number of 150-250 active TB cases to be found in order to have enough cases to first train the neural network (with at least 500 - 1000 healthy individuals and a 100 active TB cases) and then perform the blind predictions on the rest of the participants to establish sensitivity and specificity of the AeoNose™.

The study consists of one primary visit and, in case of suspicion of presumptive TB but no confirmed TB or alternative diagnosis, two follow-up visits after three and six months respectively. The estimated total study duration will be from February 2020 to May 2021. The study settingwill be the Buen Pastor, Esperanza and Tacumbú prisons in Asunción, Paraguay Required condition to perform the study in each of these three institutions is safety for the study team and also the guards and prisoners. In case of unstable conditions we will look for an alternative penal institution.

#### Start

The entire prison population and all employees will be informed on the upcoming screening operation by prison authorities, prison health care workers and trained prison health promotors. Participants will be educated on the topic of TB and upcoming study through an awareness campaign before the start of the study.

#### Visit 1.

- 1. Participants will watch an animation (video) with voice-over in Spanish, Guarani or Portuguese with general information on TB and an explanation of the study procedures. Each participant will be offered to be tested voluntarily for HIV by PRONASIDA. An independent volunteer witness is present in the room to guarantee that the participant has understood the information correctly and is able to ask questions if necessary. Participants may then decide to sign informed consent using signature or fingerprint. Individuals can also decline participation, or take time to consider their participation and return later.
- 2. After providing informed consent, a study nurse will take vital signs (blood pressure, pulse and axillary temperature) and measure the participants weight, height, temperature, middle upper arm circumference, as well as ask for smoking habits, alcohol and/or drug. Co-morbidities, medication and food intake (4 hours prior to testing) will be recorded in the digital case record form. If the participant agrees a HIV rapid test will be performed using a finger prick blood sample. Participants with a positive result will be notified and referred to the national HIV program (PRONASIDA) for final diagnosis and treatment according to national HIV guidelines.
- At the third station, a technician will perform the CXR and will process the digital image with CAD4TB™ software. A TB likelihood output score is presented within minutes.
- At the fourth station, a technician will take a breath sample with an AeoNose™ device during 5 minutes in a room free of gasses and odours.
- 5. At the fifth station, a doctor will first take a history of symptoms and will then examine the participant for signs of TB:
  - o Healthy / ill
  - Cough (15 days or longer)
  - Sputum or haemoptysis
  - Weight loss
  - Fever (continuous or intermittent)
  - Night sweats
  - o Chest pain

- Dyspnea / shortness of breath
- o Loss of appetite
- o Lymphadenopathy
- Pulmonary auscultation
- Abdominal distension
- Anaemic conjunctivae

Also the dental status of the participants will be assessed.

The digital CXR image will be analysed by CAD4TB® and the doctor will interprete the CAD4TB® output score and check the CXR for alternative diagnosis. All the findings by the study doctor will be recorded in the digital case record form. At the end of this visit the doctor will decide on health status of the participant: either the participant is considered healthy or a presumptive TB case.

For healthy participants the study ends after this 5th station.

- 6. Presumptive TB cases (see 6.1.1 Case definitions) will be asked to produce two sputum samples outside, preferably in the open air. Sputum can be either be produced spontaneously or via sputum induction with nebulized saline. Saline solution will be nebulized using a portable nebulizer. Sputum samples can deposited in standard containers. Samples will be stored in a cool box and transported to the laboratory the same day. Samples will then be processed and analysed by the National Reference Laboratory, Laboratory San Alfonso and IICS using GeneXpert® molecular testing and MGIT mycobacterial culture.
- 7. All participants will be educated about the importance of seeking medical care if symptoms compatible with TB emerge at any time.
- 8. In case a participant is passively identified with TB during the study period by the prison health services or PNCT, the study researchers will be notified. Clinical and microbiological data will be shared based on informed consent given by the participant.

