#### Referral of TB cases and non-TB illness

In case of a positive culture result or GeneXpert® with *Mycobacterium tuberculosis*, the participant will be informed and the PNCT will be notified through the prison authorities. GeneXpert® will provide a test result within 24 hours.

In compliance with the current Paraguayan national TB treatment guidelines, established TB cases will start anti-tuberculous therapy and will be followed-up by the PNCT and prison health service.

For presumptive TB case with signs of severe illness but a negative GeneXpert® result, the PNCT and the prison health service will be notified. The prison health service and PNCT may decide whether it is justified to start empiric treatment for TB. This decision will be made available to the investigators who will review these cases afterwards to categorize them according to the formal case definitions.

If a participant presents to the study doctors with signs and symptoms compatible with severe illness, the prison health service will directly be notified in order to take an appropriate action.

If the digital CXR shows pathological abnormalities not being consistent with tuberculosis, the participant will be informed and referred to the prison health service.

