## AND / OR

Any participant with CAD4TB output score above the threshold level (to be determined), or presenting with CXR abnormalities as judged compatible with TB by the study doctor.

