#### 8.1 Primary study parameter(s)

Primary study parameters are the number of TB cases cases by CAD4TB® CXR analysis and AeoNose™ breath sampling.

A binary assessment of the presence or absence of illness has four possible outcomes: true positives (TP), false positives (FP), true negatives (TN) and false negatives (FN). The relationship of the four outcomes is the basis of sensitivity and specificity analysis which determines the accuracy and predictive value of a diagnostic tool.

*True positive:* A positive test result in a confirmed TB case.

*False positive*: A positive test result with negative sputum results and no confirmed TB during follow-up.

*True negative*: A negative test result with no confirmed TB during follow-up. *False negative*: A negative test result with confirmed TB during follow-up.

Receiver operating characteristics (ROC) will be generated using an ROC package, and bootstrapping to generate confidence intervals in the ROC plot. T-testing or McNemar's test will be used to compute P values when comparing the sensitivity of conventional screening and CAD4TB® and AeoNose™ at assumed levels of specificity. We will also use multivariate analysis to analyse influences of different combinations of participant characteristics.

CAD4TB®: The collection of digital CXR images will be analysed and compared to presumptive and confirmed cases. The number of true/false positives and negatives will be used to calculate sensitivity and specificity as described above. The predictive value of the test will be analysed.

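### The Visit 1 sputum rule for a participant above the CAD4TB threshold can be read two ways, and the section 8.1 definitions leave a test-positive participant without sputum in no cell, which can only raise specificity

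*Protocol*

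**What the plan says.** **Who gives sputum.** Section 6.1.1 lists alternative routes to presumptive TB. One is symptoms or signs in the doctor's judgement. Another is "Any participant with CAD4TB output score above the threshold level (to be determined), or presenting with CXR abnormalities" that the doctor finds compatible with TB. The doctor's judgement is attached to symptoms, signs and film abnormalities, not to the score.

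In section 3, Visit 1, step 5, the doctor interprets the score and is to "check the CXR for alternative diagnosis". Then "the doctor will decide on health status of the participant: either the participant is considered healthy or a presumptive TB case". For those called healthy the study ends there. Step 6 takes sputum from presumptive cases and cross-refers to 6.1.1.

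The section 3 paragraph on referral adds: "If the digital CXR shows pathological abnormalities not being consistent with tuberculosis, the participant will be informed and referred to the prison health service". It does not mention sputum.

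**How results are classified.** Section 8.1 defines a false positive as "A positive test result with negative sputum results and no confirmed TB during follow-up". A true negative needs only a negative test and no TB confirmed over follow-up; sputum does not enter.

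**Planning figure.** The Summary states: "In case of presumptive TB (estimated 20-30% of participants) two sputum samples will be taken".

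**The concern.** There are two linked difficulties.

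First, take a participant whose score is above the threshold but whose film the doctor attributes to another disease. Under 6.1.1 this person is presumptive and gives sputum. Under step 5 the doctor could call the same person healthy, and then there is no sputum and no further visit. Doctors working in three prisons could follow the text in good faith and act differently. Whether the reference test is done would then depend on a judgement made by someone who has seen the index test result.

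Second, whichever rule was meant, section 8.1 has no cell for a test-positive participant without a sputum result. CAD4TB accuracy belongs to the primary objectives, and section 8.1 plans sensitivity, specificity and predictive value from these four cells. A definition that can lose test positives but not test negatives pushes specificity in one direction only.

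**Working it through.** **1. The sputum rule, side by side**

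| Situation | Section 6.1.1 | Visit 1, step 5 | Referral paragraph |
|---|---|---|---|
| Score above threshold, film read as non-TB | Presumptive, so sputum | Doctor decides; if healthy, study ends | Inform and refer; silent on sputum |

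The cross-reference in step 6 permits a reading in which the doctor merely applies 6.1.1. No sentence says so, and interpreting the score and looking for another diagnosis suggest discretion.

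**2. The four cells.** Take a CAD4TB-positive participant with no sputum result and no confirmed TB:

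- true positive: no, TB is not confirmed;
- false positive: no, there is no negative sputum;
- true negative or false negative: no, the test is positive.

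Two kinds of participant can arrive here: those called healthy at step 5, and presumptive cases who never produce sputum. The protocol foresees the latter, since it follows up those unable to produce sputum. Anyone who later gives a negative sample at three or six months does fit the false-positive cell.

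**3. Base figures.** The protocol's expected case count reproduces: 5000 × 0.03 = 150 and 5000 × 0.05 = 250. For illustration I take 5000 screened and 200 TB cases, leaving 4800 without TB.

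**4. Effect on specificity.** True specificity is TN / (TN + FP). If a fraction f of the non-TB positives has no sputum and drops out, the apparent value is TN / (TN + FP × (1 − f)). The protocol gives no f; 10-50% is an assumption. Section 1 quotes 70% specificity at 95% sensitivity, so TN = 0.70 × 4800 = 3360 and FP = 1440.

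- f = 0: 3360 / 4800 = 70.0%
- f = 10%: 3360 / (3360 + 1296) = 72.2%
- f = 25%: 3360 / (3360 + 1080) = 75.7%
- f = 50%: 3360 / (3360 + 720) = 82.4%

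Other assumed true specificities, for f = 10%, 25% and 50%:

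- 80%: 81.6%, 84.2%, 88.9%
- 90%: 90.9%, 92.3%, 94.7%

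The number of TB cases cancels from the ratio, so 150 or 250 cases give the same results.

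**5. Does the 20-30% figure show which rule was meant?** At 95%/70%, CAD4TB alone flags 0.95 × 200 + 0.30 × 4800 = 190 + 1440 = 1630, and 1630 / 5000 = 32.6%. At 95% and an assumed 80% specificity it flags 190 + 960 = 1150, or 23.0%. Section 1 makes the operating point depend on the threshold, and 6.1.1 leaves the threshold open. The planning figure therefore settles nothing either way.

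**The case against.** The best defence is that the protocol states the sputum rule once. Step 6 points to 6.1.1, so the doctor's decision at step 5 is just the application of that definition, and interpreting the score may mean no more than comparing it with the threshold. This reading is available. It weakens the claim of a flat contradiction, but it does not make the text unambiguous.

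Section 8.1 also says that a binary assessment has four outcomes, and section 8 ends in a final diagnosis of healthy or TB case. An analyst guided by these could count a CAD4TB-positive participant called healthy as a false positive, and specificity would then stay at 70.0%. That is sensible, but it departs from the false-positive definition as written.

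Three stronger inferences are tempting and should not be drawn:

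- *That the referral paragraph withholds sputum from participants with non-TB films.* It is silent. Referral and sputum can both happen.
- *That the 20-30% presumptive share is wrong.* It exceeds the range only at the 95%/70% point, to which the study is not committed.
- *That specificity will be inflated by a known amount.* Inflation needs positives without sputum and a literal use of section 8.1. No passage gives a rate for the first.

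Nor is TB among unsampled positives necessarily lost: step 8 passes passively detected cases to the researchers, although this is only partial protection.

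Finally, methods for unverified participants are commonly left to a SAP. That holds for the sensitivity analysis. It does not hold for the visit procedure and cell definitions, which this protocol fixes itself, and no later plan can recover sputum that was never taken.

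**Conclusion.** The point holds in two parts. The sputum rule for participants above the CAD4TB threshold is ambiguous between section 6.1.1 and Visit 1, step 5, and the referral paragraph leaves open what happens when the film is judged non-TB. Independently, the section 8.1 definitions are asymmetric and leave test-positive participants without sputum or confirmed TB unclassified.

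If the definitions are applied literally, the direction of the error is certain: dropping non-TB positives from TN / (TN + FP) can only raise specificity. The size is not. The shift from 70% to about 72-82% rests on an assumed 10-50% of non-TB positives lacking sputum and on a true specificity of 70%. At 80% or 90% true specificity the shift is smaller. It is zero if every CAD4TB positive is sampled or if unsampled positives are counted as false positives.

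**What to change.** 1. Reconcile section 6.1.1, Visit 1 steps 5 and 6, and the referral paragraph into one sputum rule that every doctor applies in the same way. It should say what happens when the score is above the threshold and the film is judged non-TB. Which rule to adopt is for the sponsor.
2. Amend the false-positive definition in section 8.1 so that test-positive participants without sputum and without TB confirmed during follow-up stay in the denominator, counted as false positives in the main estimate. Report their number as unverified. The definition serves both tests, so the amendment also gives a cell to AeoNose positives who were never sampled.
3. Add a sensitivity analysis that corrects for verification bias. Its details can sit in the SAP.
4. Restate the expected presumptive share once the threshold and the rule are set.

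No new CRF item is needed: the CAD4TB score and the doctor's findings are already recorded, so threshold status can be derived. The cost is protocol wording and one extra analysis. Reported specificity may be less favourable, and the main estimate will be conservative to the extent that some unverified positives do have TB.
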